### Preliminary Studies:

We have assembled a highly qualified team of investigators with extensive expertise in performing exercise rehabilitation studies in older veterans. Seventeen older ( $75.6 \pm 4.5$ ) adults with a history of falls were recruited for a preliminary study utilizing MMBI. Subjects performed the intervention in our exercise facility 3 times/week for 16 weeks and were instructed in a home regimen to continue after completion of the center-based portion of the intervention. 16 out of 17 individuals completed all portions of the study with > 90% adherence to the protocol. Six of the 16 fell at least once during the 4 month study, and an additional six subjects reported at least 1 near fall. Four-square step times (FSST) in those who fell were significantly slower ( $12.7 \pm 6.5$  seconds) than in those who did not fall ( $5.98 \pm 2.12$  seconds), ( $p=0.009$ ). Notably, however, these individuals also had the greatest improvement with the intervention. After 16 weeks of MMBI scores on the functional gait assessment (FGA) increased by 12% and the time to complete the FSST decreased by 24%. Individuals with FSST > 10 seconds at baseline made even greater improvements of 40-50% on the FSST and FGA. Furthermore these improvements were maintained for 4 months after the completion of the exercise program. These findings warrant the application of our MMBI program to a larger study of greater duration with an active comparison group, particularly in those with a FSST > 10 seconds at baseline.

Parameter (N=16)	Baseline (mean $\pm$ SD)	16 week Post-intervention(mean $\pm$ SD)	P value
BMI (kg/m  )	26.9 $\pm$ 3.2	27.0 $\pm$ 3.2	0.40
Four-square (sec)	8.5 $\pm$ 5.3	6.1 $\pm$ 2.7	0.04
Functional gait assessment*	22.7 $\pm$ 5.9	25.5 $\pm$ 5.2	0.01
Leg extension strength	278.80 $\pm$ 110.5	299.00 $\pm$ 114.9	0.05

\*N of 8, measurement only performed on second cohort

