Aim 1: Primary Outcome Measures: Four-Square Step Test (FSST) and Functional Gait Assessment Tests (FGA). The primary outcome measures will be the change from baseline to 24 weeks in the FSST and the FGA. The FSST is a test of dynamic balance ability that assesses an individual's ability to change directions while stepping. Subjects will be timed as they step over four canes set-up in a cross on the floor. Participants will be closely guarded as they perform the test to prevent any falls. The FSST is an ideal outcome measure as it assesses the ability of an individual to dynamically maintain an upright posture while changing directions and weight shifting. It has excellent inter-rater reliability (ICC=0.99), test-retest reliability (ICC=.98), sensitivity (92%) and specificity (93%) in older adults. Older adults who take > 15 seconds to complete the task are at increased risk for multiple falls.

The FGA will also be used as a primary measure of dynamic mobility and balance and to assess fall risk. The FGA is a 10-item clinical gait test that is based on the dynamic gait index (DGI). It tests higher level dynamic gait activities that are part of daily functional mobility such as turning safely, walking at speeds required to safely cross a street, the ability to walk with head turns, gait with a narrow base of support and ambulating backwards. Each of the ten items is scored 0 to 3, with total scores ranging from 0 to 30. Scores below 22 are predictive of future falls. The FGA has excellent inter-rater reliability (ICC=.93) and predictive validity for falls. The FGA is an ideal outcome for this balance study in older veterans.

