#### Sample Size Determination and Power Analysis

This is a pilot study with an aim towards developing estimates for effect sizes that can be used to design a larger, confirmatory randomized clinical trial. A sample size of 20 per group will allow us to detect a difference of 25% between groups for our primary outcome of the four square step test. We will enroll 40 subjects. Typical attrition rates are 25 to 30%, primarily due to time conflicts and development of non-study related medical problems. In our preliminary studies, MMBI decreased the time to complete the four square test by 24%, with even greater improvements in the frailest subjects. Time to complete the four-square test has been shown to be an excellent biomarker for fall risk.

For our second exploratory Aim the outcome will be the rate of falls and the proportion of fallers during the intervention. The sample size estimate is determined primarily by three factors; the baseline rate of falls in the study population, the duration of follow-up, and the differential impact of the two interventions on the fall rates. For example in the Lifestyle integrated Functional Exercise (LiFE) program, which embedded balance and lower limb strength training into habitual daily routines there was a statistically significant 31% reduction in fall rates (1.66 per person years) compared to controls (2.28 per person years), whereas the structured lower limb strength and balance exercises had a non-significant 19% reduction (1.90 per person years) in fall rate compared with the controls. Based on this and other literature we estimate that setting the power at 80%, alpha at 5% and with a drop-out rate of 20%, a sample size of 90 is required in each group to detect a clinically significant difference of 25% reduction in falls frequency between the two groups. Due to the budgetary limitations and duration of this VA SPIRE grant it is not feasible for us to enroll and study 180 subjects. Thus we recognize that we might not have sufficient power to see a difference in fall rate and number of falls between groups. Results from this study will be used to power a larger randomized clinical trial that will examine the effectiveness of the two interventions to reduce rate of falls and risk of falling in older veterans at high risk for falls.

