Statistical Analysis: Data analyses will be performed using SAS. We will first perform an exploratory analysis to look for extreme values to make sure they are not the result of data entry error. All analyses will be conducted using the intention-to-treat principle. Statistical significance will be at an alpha of 0.05 (two-tailed). Demographic and clinical characteristics at baseline will be summarized with standard descriptive statistics.

For aim 1, to compare changes (defined as 24-week value minus baseline value) in mobility, balance and strength between our two groups (tai chi and MMBI) after 24 weeks of intervention we will use ANOVA for all continuous outcome measures (change=group).

For Aim 2 We will use Poisson regression (or, if the data are overdispersed Quasipoisson or negative binomial regression) to compare the number of falls in our two experimental groups. This methodology has been employed in the LiFe trial and other studies.

Project time line: Prior to the start of the funding, we will obtain regulatory approvals from the IRB and VA R&DC. We will recruit 3 sets of intervention cohorts. Recruitment and baseline testing of the first cohort will start at the start of the funding period and they will enter intervention at month 3. While this first cohort is undergoing intervention we will recruit and perform baseline testing on the second cohort who will enter the intervention approximately 6 months after the start of the study. Post intervention testing on the first cohort will commence at 9 months. Recruitment for the third cohort will be done while the second cohort is in intervention and the third cohort will start their intervention at 9 months. During months 21 to 24 we will perform data analysis, and start writing manuscripts. We have used a similar strategy of staggered cohorts in prior studies. The study will be completed in a two years.

Anticipated Results and Alternate Findings: While we do not anticipate that Tai Chi will result in larger improvements in balance and falls than MMBI it is possible. The strength, balance, and gait tests that we are performing allow us to evaluate the contribution each makes to improving balance. This information can be used to design a future larger study aimed at decreasing falls.

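### The FSST target is an undefined 25%, and the planned unadjusted comparison of changes in seconds is valid but inefficient for a time whose spread rises with its mean

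*Combined protocol and SAP*

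**What the plan says.** The Aim 1 outcome section states: "The primary outcome measures will be the change from baseline to 24 weeks in the FSST and the FGA". The Statistical Analysis section plans "to compare changes (defined as 24-week value minus baseline value) in mobility, balance and strength between our two groups", using ANOVA with group as the only term for every continuous outcome, at two-sided 0.05. It names no baseline covariate and no transformation. Extreme values are checked only as possible data-entry errors.

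The sample-size section states: "A sample size of 20 per group will allow us to detect a difference of 25% between groups". It gives no reference mean, SD or power for this statement; the 80% power in the same section belongs to the falls calculation for Aim 2. Beside the target stands a 24% pilot decrease in FSST time within one group.

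Preliminary Studies reports FSST both ways. Its table is in seconds (8.5, SD 5.3, falling to 6.1, SD 2.7; P = 0.04; n = 16), as are fallers (12.7, SD 6.5) and non-fallers (5.98, SD 2.12). The text uses percentages, for example "Individuals with FSST > 10 seconds at baseline made even greater improvements of 40-50% on the FSST and FGA". Entry to this trial requires FSST above 10 s.

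**The concern.** The target is a percentage, the test is on seconds, and nothing connects them. A 25% reduction is 2.5 s for someone who starts at 10 s and 6 s for someone who starts at 24 s. If the effect is roughly proportional, a few slow participants drive both the mean change in seconds and its SD. The entry rule removes the fast end of the distribution and keeps the slow tail. A change score with no baseline term also carries baseline variation into its standard error.

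At stake are the power of a small trial on a primary outcome, and the usefulness of its effect estimate, since the sample-size section says the trial is meant to supply effect sizes for a larger one.

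**Working it through.** **1. The plan's own figure.** The 20 per group cannot be reproduced, because SD, power and scale are missing. Assume 80% power, two-sided 0.05: n per arm = 2 × (1.960 + 0.842)² × SD²/δ² = 15.70 × SD²/δ². With n = 20 this requires an SD of change of at most 28% of the reference mean (seconds), or a log-change SD of at most 0.325 (ratio of 0.75, ln = −0.288). Two readings in seconds come close to 20:
- 25% of 10 s with SD 2.7 s: 15.70 × 7.29/6.25 = 18.3, so 19.
- 25% of 15 s with SD 4.27 s (step 3): 15.70 × 18.23/14.06 = 20.4, so 21.

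A target in seconds therefore cannot be excluded.

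**2. Spread against mean in the pilot.**
- Six fallers and ten others pool to (6 × 12.7 + 10 × 5.98)/16 = 8.50 s. The pooled SD is √[(5 × 6.5² + 9 × 2.12² + 6 × 4.2² + 10 × 2.52²)/15] = 5.30 s. Both match the table, so these are baseline values of the same 16 people.
- SDs of the two subgroups: 6.5/2.12 = 3.1-fold apart. CVs: 0.51 and 0.35, 1.4-fold apart.
- Pre and post CVs: 5.3/8.5 = 0.62 and 2.7/6.1 = 0.44.
- Mean minus 2 SD at baseline is 8.5 − 10.6 = −2.1 s, impossible for a time, so the distribution must be right-skewed.

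**3. Pilot-based model.** Assume that the P of 0.04 is from a paired t-test: t on 15 df = 2.25, so the SD of change is 2.4 × √16/2.25 = 4.27 s and the pre-post correlation is (5.3² + 2.7² − 4.27²)/(2 × 5.3 × 2.7) = 0.60. Lognormal conversion gives log SDs of 0.573 and 0.423, log correlation 0.63, slope 0.47 and residual SD 0.328.

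**4. Power, baseline restricted to above 10 s, true ratio 0.75, 20 per arm (simulation).**

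| Analysis | Pilot-based (slope 0.47) | Proportional change, log SD 0.30 |
|---|---|---|
| Change in seconds (as planned) | 27% to 55% | 78% |
| Change in log seconds | 69% | 84% |
| ANCOVA, seconds | 73% | 78% |
| ANCOVA, log seconds | 76% | 83% |

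The first row of the pilot-based column depends on the assumed Tai Chi mean at 24 weeks. Power is 27% if that arm is centred on the pilot's post-test mean, 41% if its mean is about 11 s, and about 55% if it does not change on average. The other three rows do not depend on it.

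Checks by normal approximation:
- Change in seconds at the 11 s setting (difference 2.75 s, SD 5.04 s): 2.75/5.04 × √10 − 1.96 = −0.23, so 41%.
- Log ANCOVA: 0.288/0.328 × √10 − 1.96 = 0.81, so 79%, against 76% simulated with a t-test and an estimated slope.

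**5. Source of the loss.** At the 11 s setting, adding baseline in seconds moves power from 41% to 73%, and moving to logs then adds 3 points. Logging the change score alone gives 69%, so the two remedies overlap, with adjustment the stronger. With purely proportional change, adjustment gains nothing and the scale accounts for the whole difference: 98% v 99% at log SD 0.20, 78% v 83% at 0.30, 53% v 60% at 0.40.

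**6. Sensitivity.** Across proportional or nearly proportional settings the planned test had 47% to 98% against 59% to 99% for log ANCOVA. The gap widens if the Tai Chi arm itself improves substantially: one such set (slopes 0.8 to 1.0, residual SD 0.30 to 0.40) gave 40% to 70% for change in seconds against 59% to 84% for log change. With a constant 3 s effect instead of a ratio, the pilot-based figures are 50% for change in seconds and 96% for log ANCOVA. Type I error was about 5% for every analysis.

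**The case against.** A reader might infer that the plan promises a ratio and tests something else. The documents do not support that. The 25% has no stated scale; if it means 25% of a mean in seconds, the ANOVA addresses it, and step 1 shows that such readings fit the stated sample size. Seconds are also a natural scale here: the pilot table, the entry criterion and the 15 s risk threshold all use them. What stands against the plan is that the 25% is undefined.

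A reader might also put the whole power gap down to the choice of seconds. In the pilot-based case that is wrong: an ANCOVA in seconds (73%) beats a log change score (69%).

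Nor can it be said that only a result in seconds depends on case mix. The pilot's percentage improvement was itself larger in slower participants, and the tabled means fall by 2.4/8.5 = 28% where the text says 24%.

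Finally, randomisation is stratified by FSST, this is a pilot, and skew is inferred rather than documented. Stratification does limit chance imbalance, but an ANOVA that ignores baseline does not use it to reduce the standard error. Pilot status lowers the stakes of a missed significance test, but makes a precise and well-defined effect estimate more important.

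**Conclusion.** The point holds as one of efficiency and definition, not validity. The FSST target needs a scale, and the planned analysis is a weak choice for the data that the pilot suggests. The shortfall against log ANCOVA is about 20 to 50 points in the pilot-based case (76% less 55% and less 27%), mostly recoverable by baseline adjustment alone. It is about 1 to 13 points if change is proportional or nearly so, and more if the Tai Chi arm also improves markedly. After adjustment the log scale is worth about 3 to 7 points, less where power is already near its ceiling.

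The direction was the same in every scenario run with entry above 10 s. The size is uncertain: it rests on 16 pilot participants whose mean was below this trial's entry cut-off, a lognormal shape, a paired t-test behind the P value, an assumed ratio of 0.75, an assumed Tai Chi mean at 24 weeks, and 20 per arm analysed. The point concerns FSST only.

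**What to change.** In Statistical Analysis, make the FSST analysis an ANCOVA of log 24-week time on group and log baseline time. Report the MMBI/Tai Chi ratio of geometric means with its 95% CI, and keep change in seconds as a descriptive summary. In the sample-size section, define the 25% on the same scale, for example as a ratio of 0.75, and state the assumed SD and power. FGA and strength stay on their own scales.

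The cost is about one sentence in each section and no new data. The small downside is that the primary FSST result is read as a percentage rather than in seconds.

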### Methods/Study Procedures:

Approach: We will enroll 56 older community dwelling veterans (age > 65 years) with a fall in the past year and evidence of balance dysfunction (FSST > 10 seconds). Our preliminary findings suggest that those with higher FSST benefit the most from MMBI. After baseline testing, individuals will be randomized to either MMBI or to a Tai Chi intervention. All participants will participate in a group exercise class in their assigned intervention for 1 hour, 3 times per week for 24 weeks. To promote camaraderie and accountability among subjects they will be enrolled in intervention cohorts of 8 to 10 subjects. At randomization subjects will be stratified first by gender then by FSST. Assessments will occur at baseline and after completion of the intervention and will include balance, mobility and fall risk, lower extremity strength, and muscle composition (total body DXA scan, hip and thigh CT scan). All participants will be followed from initial enrollment until 6 months after completion of the post-intervention testing (6 months follow up) utilizing calendar diaries, post-cards and monthly phone calls from the study coordinator to determine the number of falls, near falls, injuries and fall related medical visits.

Recruitment and Screening: A variety of methods will be used to recruit older veterans with a history of a fall in the last year, including the Baltimore GRECC subject recruitment registry, advertisements, provider referrals, community outreach, outpatient clinics and the emergency department at the VAMHCS. The use of multiple recruitment strategies will allow us to maximize our outreach to a diversity of veterans including those who have yet to seek routine care at the VA. A fall will be defined as any event that resulted in a person coming to rest unintentionally on the ground or other lower level. Prospective studies have demonstrated that older adults with a history of falls are more likely to experience subsequent falls. Exclusion criteria will include: dementia, unstable angina, poorly controlled hypertension, active substance abuse, poorly controlled diabetes, progressive neurodegenerative disease, and any other major orthopedic or health condition that would limit ability to safely exercise (see human subjects section for more

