details). Interested individuals will initially undergo a telephone screen by the project coordinator to assess eligibility for the study using our inclusion/exclusion criteria. Potential participants who pass the phone screen will be invited to our facility. After informed consent, a history and physical will be performed. Based on prior studies we anticipated that 20 to 30% of those brought in for the screening evaluations will not qualify for the study (screening failures).

After the completion of all screening tests eligible participants will be scheduled for baseline testing at the Baltimore GRECC and VAMHC Human Performance Laboratory consisting of: 1) balance testing (Four-square step test), 2) mobility and fall risk assessment (functional gait assessment, clinical gait assessment and gait variability on a GAITrite and 6 minute walk), 3) questionnaires (falls efficacy and ABC) 4) lower extremity isometric strength testing (Biodex), and 6) total body DXA scan, and a CT scan of the abdomen, hips and thighs for determination of lower extremity and core muscle composition. All testing will be conducted by individuals that are blinded to group assignment and not involved with group training.

After completion of baseline testing the veterans will be randomized to either MMBI or a Tai Chi intervention. The MMBI and Tai Chi intervention sessions will be held at different times of the day to minimize cross-contamination between the two groups, with time alternating with different cohorts to minimize any inadvertent training effect due to time of day.

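### Aim 1 compares raw change between arms without adjusting for baseline or the stratifiers; ANCOVA should be more precise for FSST, by an amount the documents cannot fix

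*Combined protocol and SAP*

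**What the plan says.** The Statistical Analysis paragraph for Aim 1 defines change as the 24-week value minus baseline and gives one model: "after 24 weeks of intervention we will use ANOVA for all continuous outcome measures (change=group". No baseline covariate, gender term or FSST stratum is named there or elsewhere.

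Four other places bear on this:

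- The Approach paragraph of Methods/Study Procedures says: "At randomization subjects will be stratified first by gender then by FSST". It gives no cut-points or blocking scheme.
- The Aim 1 primary outcome text says: "The primary outcome measures will be the change from baseline to 24 weeks in the FSST and the FGA".
- On timing, Methods/Study Procedures says: "After completion of baseline testing the veterans will be randomized to either MMBI or a Tai Chi intervention". The covariates will therefore exist for everyone randomised.
- Preliminary Studies reports: "Individuals with FSST > 10 seconds at baseline made even greater improvements of 40-50% on the FSST and FGA". The fall in FSST time across the whole pilot was 24%. The Approach paragraph draws the inference: "Our preliminary findings suggest that those with higher FSST benefit the most from MMBI".

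**The concern.** The design balances the arms on a variable expected to predict the outcome, and the analysis then leaves that variable out. A change score is fully efficient only if the 24-week value rises one for one with baseline. The protocol's own pilot suggests that for FSST it does not. Baseline spread that could be explained then stays in the error term, and the confidence interval is wider than it need be.

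Interval width matters here because the sample size section describes the trial as a pilot with "an aim towards developing estimates for effect sizes that can be used to design a larger, confirmatory randomized clinical trial". FSST is a primary outcome, and the number analysed will be small.

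**Working it through.** **1. The plan's own figure.** The sample size section says 20 per group can detect a 25% FSST difference. It gives no SD, power or base for the 25%. At an assumed 80% power, 20 per group needs a standardised difference of 0.886. That is an SD of 2.40 s if the base is 8.5 s, 2.82 s if 10 s, or 3.58 s if 12.7 s. The figure cannot be checked and does not show which model was assumed.

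**2. The two models.** Let B be baseline with variance V, and let the 24-week value be Y = a + tG + bB + e, where G is arm and Var(e) = s². Then Y − B = a + tG + (b − 1)B + e.

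- Error variance with arm alone: (1 − b)²V + s².
- Error variance with ANCOVA: s².
- Proportional reduction: (1 − b)²V / [(1 − b)²V + s²]. It is zero when b = 1.
- The arm effect t is the same whether Y or Y − B is the response, once B is in the model.

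**3. Slope from the pilot table** (paired t-test assumed). The SD of change is mean change × √N / t; r follows from the three SDs; slope = r × SD(post)/SD(baseline); ANCOVA SD = SD(post) × √(1 − r²).

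| Outcome | SD of change | r | ANCOVA SD | Variance ratio |
|---|---|---|---|---|
| FSST (N=16) | 2.4 × 4 / 2.249 = 4.27 | 0.60 | 2.16 | 0.256 |
| FGA (N=8) | 2.8 × √8 / 3.499 = 2.26 | 0.92 | 1.98 | 0.767 |
| Leg extension (N=16) | 20.2 × 4 / 2.131 = 37.9 | 0.944 | 37.9 | 0.997 |

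The FSST slope is 0.60 × 2.7/5.3 = 0.31. The paired-test assumption is not critical for FSST: the two SDs alone cap the slope at 2.7/5.3 = 0.51 and the variance ratio at (2.7/5.3)² = 0.26.

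**4. The trial population.** The trial admits only FSST above 10 s, so V may be smaller than in the pilot. Variance reduction for assumed baseline SDs:

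| Slope b, error SD s | SD 2 | SD 3 | SD 4 | SD 5.3 |
|---|---|---|---|---|
| 0.31, 2.16 (pilot) | 29% | 48% | 62% | 74% |
| 0.6, 4.24 | 3% | 7% | 12.5% | 20% |
| 0.8, 3.18 | 2% | 3% | 6% | 10% |

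Interval width scales as √(1 − reduction). At SD 2 and slope 0.31 the interval is √0.71 = 0.84 of its planned width. At SD 2 and slope 0.8 it is √0.98 = 0.99, before the lost degrees of freedom.

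**5. Effect of stratification.** With arm alone, the model charges the full (1 − b)²V to error although stratification has removed much of it from the arm difference. This was simulated with 20,000 trials per cell and independent participants. FSST above 10 s was drawn from a truncated lognormal (mean 15.0, SD 5.4), with blocks of 4 within gender by FSST, cut at the median or 15 s. All of these are assumptions.

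| Slope | Type I error, arm alone, 20 per arm | CI width, ANCOVA / arm alone, 20 per arm | Same, 14 per arm |
|---|---|---|---|
| 0.31 | 1.1–1.6% | 0.51–0.52 | 0.52 |
| 0.6 | 4.0–4.2% | 0.90–0.91 | 0.91–0.92 |
| 0.8 | 4.4–4.6% | 0.96 | 0.97 |

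ANCOVA gave 4.8–5.3%. In a companion simulation without stratification, arm alone gave 4.9–5.1%: it held its level and lost only precision.

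The 14-per-arm column reflects 25 to 30% attrition from 40 enrolled (40 × 0.70 = 28). The Approach paragraph says 56, which would leave about 20 per arm (56 × 0.70 ≈ 39).

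**6. Other outcomes.** With three covariates and an outcome unrelated to FSST (the adverse case), the width ratio at 20 and 14 per arm is 0.90 and 0.92 for FGA, and 1.03 and 1.05 for leg extension.

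**The case against.** **The planned test is legitimate.** This stands. With independent participants, change on arm alone does not exceed its nominal level. A reader might infer that the primary analysis is invalid; the documents do not support that. The issue is precision.

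**The large figures come from the wrong population.** This stands in large part. The slope of 0.31 comes from 16 MMBI participants at 16 weeks with mean FSST 8.5 s, while the trial enrols only those above 10 s. Nothing is known about the Tai Chi slope. The direction needs only a slope below 1, which the pilot supports; the size stays open.

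**Independence is itself an assumption.** This also stands. Training is in cohorts of 8 to 10. With three classes per arm and an assumed class correlation of 0.02 to 0.10, type I error for arm alone was 1.8–3.3% at slope 0.31, 5.4–9.9% at 0.6 and 5.4–12.5% at 0.8. ANCOVA ran from 6.4% to 13.6%. A reader might infer that ANCOVA secures a 5% test; it does so only without clustering. An accidentally wide standard error is not a remedy for clustering either, so this does not argue for keeping the planned model.

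**The slope may differ by arm.** In simulation with slopes 0.31 and 0.8, common-slope ANCOVA stayed at 4.9–5.2%.

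**The next trial.** A reader might invert the pilot variance ratio (1/0.256 = 3.9) and conclude that the next trial would be 3.9 times too large. The sample size section says that trial will examine falls, and nowhere says the FSST SD will size it. An ANCOVA SD could also be computed later from the same data.

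**Missing data.** The plan expects losses: "Typical attrition rates are 25 to 30%, primarily due to time conflicts and development of non-study related medical problems". A reader might count this against the change score, but ANCOVA on 24-week values loses the same people. Nor is the plan silent on the analysis set, since it states intention-to-treat.

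**Conclusion.** The point holds as one about precision, mainly for FSST. Arm alone forces a slope of 1 and omits both stratifiers, while the pilot indicates an FSST slope below 1. The test is also conservative if stratification balances FSST and participants are treated as independent.

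At 20 per arm the FSST interval narrows by about 4% at slope 0.8 and about 48% at the pilot slope, under assumed shapes, cut-points and blocking. It narrows by less if the entry floor leaves little baseline spread, and the gain vanishes as the slope approaches 1. For FGA a gain is plausible but rests on eight people. For leg extension there is none.

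Nothing here shows that the primary test is invalid or that the later falls trial would be mis-sized.

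**What to change.** In the Statistical Analysis paragraph, replace the Aim 1 model with wording such as:

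> Each continuous Aim 1 outcome will be analysed by ANCOVA of the 24-week value on arm, the baseline value of that outcome, gender and baseline FSST (entered once when FSST is the outcome). The adjusted arm difference will be reported with its 95% confidence interval. ANOVA of change on arm alone will be a sensitivity analysis.

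The definition of the primary outcomes as change can stand, because with baseline in the model both responses give the same arm difference, interval and p-value.

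The cost is a few lines of SAS and no new data. FSST loses 2 degrees of freedom (38 to 36 at 20 per arm, 26 to 24 at 14) and other outcomes lose 3. Where the slope is near 1, the interval widens slightly, by 3 to 5% on the leg extension figures.

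Clustering by exercise class and missing 24-week values need their own provisions. Clustering should be settled before the ANCOVA interval is taken at face value.
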